8.2. Prospective Group

- Undetectable plasma viral load at screening;
- CD4+ cell count > 50 cells/mm 3 ;
- Age less than 18 years old;
- Asymptomatic individuals.

9. Study Flowchart

10. Study Procedures

10.1. Retrospective Group

Procedures	*Basal	Without 24	Without 48
TCLE	Not applicable		
Inclusion and Exclusion Criteria	X		
Medical History	X		
Adverse events	During the 48 weeks		
CV HIV-1	X	X	X
CD4+ / CD8 count	X	X	X
Biochemistry	X	X	X
Hematology	X	X	X

NOTE: A window of -30/+30 days for each visit will be acceptable for collecting this data.

*In the baseline visit, results of laboratory tests up to 90 days before screening will be accepted.

10.2. Prospective Group

Procedures	Basal	Without 4	Without 8	Without 16	Without 24	Without 48
TCLE	X					
Inclusion and Exclusion Criteria	X					
Medical History	X					
Adverse events		X	X	X	X	X
CV HIV-1	X	X	X	X	X	X
CD4+ / CD8 count	X	X	X	X	X	X
Biochemistry	X	X	X	X	X	X
Hematology	X	X	X	X	X	X
Plasma Sample (Storage)	X					
Vitamin D3	X				X	X

NOTE: A window of -30/+30 days for each visit will be acceptable for collecting this data.

10.3. Basal Critical Ratings

The Informed Consent Form (TCLE) must be obtained from each potentially eligible individual (or their legal representative) by the study center staff before any study procedure. The TCLE must have been approved by the Research Ethics Committee (CEP). Upon signing up, participants will complete initial assessments to determine their eligibility. Each participant selected for evaluation of inclusion in the study will be assigned an allocation number, given sequentially in chronological order of inclusion.

10.4. Initial Evaluation Period

Participants who meet the eligibility criteria will be included after signing the TCLE.

10.6. Security Parameters

- Incidence and severity of adverse effects and laboratory abnormalities;
- Absolute values and changes in results throughout the study;
- Proportion of participants discontinuing therapy due to adverse events;
- Changes in the initial physical examination.

10.7. Toxicity Control

The occurrence of an Adverse Event (AE) during the study period will be evaluated by the investigator and classified according to the Division of AIDS (DAIDS) toxicity scales.

The safety of Dolutegravir as initial therapy in critically ill participants has not been fully defined and the investigational product may be discontinued by the investigator according to the severity of the AE. No reduction of DTG doses will be allowed. Any change in the use of DTG must be recorded in the CRF. In case there is a need to interrupt the DTG, the drug will be replaced by a PI/r.

Participants who experience a grade 1 or 2 AE will continue to receive DTG at the Investigator's discretion. Subjects who experience a Grade 3 AE may continue to use DTG if the investigator is of the opinion that the toxicity was not caused by the drug, but if the AE is found to be caused by the DTG, or if it is classified as a Grade 4, the drug should be interrupted.

10.8. Follow-up of Participants

All participants included in the protocol in the Prospective Group will be evaluated at baseline and after 4, 8, 16, 24, 36 and 48 weeks.

11. Study Duration

We estimate to recruit 92 participants over a period of 10 months. Considering the need for follow-up to 48 weeks, the total duration of the study will be 22 months. An additional two months will be spent on data analysis and manuscript preparation, giving us a total of 24 months to complete the study. The retrospective study should be

completed within the same time period. The selection of patients will be carried out considering eligible participants, consecutively, until the predicted N is reached.

12. Statistical Analysis and Justification of the Sample Size

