A recent study comparing mortality rates between low-income and high-income countries in participants with AIDS starting ARV therapy demonstrated that the risk ratio for early death was 4.3 times higher (95% CI: 1.6 - 11 .8), in poorer countries, but dropped to 1.5 after seven months of therapy (6). Furthermore, another report comparing mortality rates among participants with AIDS in Brazil and the USA showed that individuals with CD4+ cell counts below 50 cells/mm³ had a 4.8 times greater risk of death after starting ART and the proportion of early deaths in the first three months was significantly higher for Brazilian participants compared to Americans (14).

In Brazil and other developing countries, there is still a large proportion of participants with AIDS who are diagnosed with AIDS, or who only seek health care for HIV infection in the final course of the illness. While a median first CD4+ cell count below 200 is a frequent finding for most countries in the world, it is expected to be even lower for participants living in resource-limited countries, making the problem of early mortality an issue. important concern.

Dolutegravir (DTG), an HIV-1 integrase inhibitor, is a potent and safe antiretroviral drug (14). Available evidence suggests that drugs in this class promote a more rapid reduction in HIV-1 plasma viremia, and a greater increase in CD4+ cell count, compared to EFV (15,16).

We propose to compare the impact of DTG versus EFV on early mortality rates in critically ill participants starting antiretroviral therapy (CD4+ <50 cells/mm³).

4. Study Design

This is a pilot, open-label study to prospectively assess the rate of early all-cause mortality in participants initiating ART with DTG-based regimens. Retrospectively, the medical records of participants who used EFV in the years 2014-2016 will be reviewed for comparison purposes.

5. Local

The study will be conducted by FBaI - Fundação Bahiana de Infectologia (Bahia) - Investigator: [name], and will include 4 additional sites in different Brazilian cities (Manaus, Natal, Florianópolis, and Porto Alegre)

6. Sample size

The total number of participants included in each study arm will be 92. The calculation of this sample size is detailed in the SAMPLE SIZE section.

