12.1. Sample Size Justification

Mortality rates are quite variable, depending on region, specific study, and population.

Most studies from African countries have shown that mortality in the first 3 months of ART for participants with CD4+ cells under the threshold of 50 cells/mm³ is generally greater than 30%, and may reach 52% in some reports.

On the other hand, in developed countries, most deaths in such a population usually occur after 7 months of therapy and the mortality rate is just as low (1.8% for the first year of treatment).

We estimated that early mortality for participants included in the EFV arm would be similar to the rates detected in African countries (around 30%). We hypothesize that participants using DTG-based regimens would benefit from faster recovery of CD4+ cell count and that they behave like those individuals starting antiretroviral therapy in developed countries (mortality rate around 2%).

Considering a lower limit of 2% (DTG arm) and an upper limit of 25% (EFV arm), a 95% CI and 80% power to detect differences between groups, it would be necessary to treat a total of 84 participants (42 on each arm). Adding 10% for dropouts, this would result in a total of 92 subjects (46 in each arm).

With the recent changes in treatment recommendations, all 92 participants will receive DTG. Participants who used EFV will be retrospectively evaluated, through the review of medical records, in an identical number (92 participants).

This will be an exploratory pilot study.

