12.2. Statistical Analysis Plan

12.3. General considerations

intent-to-treat population , defined as all participants who are randomized to treatment. With the exception of the Primary Efficacy Endpoint Analysis, percentage responders to

the intention-to-treat population, missing data will not be estimated or carried forward in any statistical analyses.

All comparisons of treatment groups will be performed using two-tailed tests at a significance level of 0.05 ($p < 0.05$). The null hypothesis for all analyzes is that there is no difference between treatment groups.

All summaries, statistical analyzes and individual participant registration data described below will be provided in separate attachments. Separate listings will be provided for each of the treatment groups in the intent-to-treat population.

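### No rule aligns the site mix of the DTG and EFV groups, so mortality differences between sites could appear as a drug effect in either direction

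*Protocol*

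**What the plan says.** The two groups are not randomised against each other. Protocol section 12.1 states that "all 92 participants will receive DTG" and that the same number of EFV patients will be taken from records. Section 4 describes the comparator in one clause: "the medical records of participants who used EFV in the years 2014-2016 will be reviewed for comparison purposes".

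Section 5 names the Bahia centre and four further sites, in Manaus, Natal, Florianópolis and Porto Alegre. It gives this list for the study as a whole and does not say which sites supply which group.

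Section 11 allows 10 months to recruit the 92 DTG participants, says that the retrospective part should finish within the same overall period, and then gives the selection rule: "The selection of patients will be carried out considering eligible participants, consecutively, until the predicted N is reached". The stopping point is an overall number. No number per site is set for either group.

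The retrospective criteria in 7.1 and 8.1 cover HIV confirmation, years of EFV use, CD4+ count, age, viral load and symptoms, but not site. Table 1, in both the protocol (12.5) and the SAP, checks comparability on age, viral load and CD4+ only. Table 2 in both documents compares the proportion of deaths by a chi-square test, with no stratification or adjustment. Section 12.3 applies "two-tailed tests at a significance level of 0.05" to all comparisons between the groups.

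**The concern.** Without randomisation, the site mix of each group is whatever the selection process produces. The DTG group fills as patients present over 10 months. The EFV group fills from records that already exist. Both stop at a total, so the two groups could end with quite different shares of patients from each city.

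If one-year mortality differs among the sites for reasons unrelated to the drug, such as case mix or access to inpatient care, that difference enters the DTG-EFV comparison directly. It could favour either drug. All-cause mortality in the first year is the primary outcome in section 6.1, and section 2 hypothesises lower early mortality with DTG, so a spurious difference would bear on the main conclusion. As planned, no table would show the imbalance and no test would remove it.

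**Working it through.** **1. The plan's own figure.** Section 12.1 gives: "Considering a lower limit of 2% (DTG arm) and an upper limit of 25% (EFV arm), a 95% CI and 80% power", and from this 42 per arm. The two-proportion formula, with p1 = 0.02, p2 = 0.25, d = 0.23 and mean proportion 0.135, gives

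n' = [1.96 × √(2 × 0.135 × 0.865) + 0.842 × √(0.02 × 0.98 + 0.25 × 0.75)]² / 0.23² ≈ 33.4.

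The continuity correction, n = (n'/4) × [1 + √(1 + 4/(n'd))]², gives 41.7, so 42 per arm, as stated. Adding 10% gives 42 × 1.1 = 46.2, stated as 46. With 92 per group, nominal power for 2% against 25% is 99.7%. Sample size is therefore not the problem here.

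**2. How site mix enters the comparison.** Let p_s be mortality at site s, the same under either drug, and let w_s be the share of a group that comes from site s. A group's expected mortality is Σ w_s p_s. With no drug effect, the expected EFV minus DTG difference is Σ (w_s,EFV − w_s,DTG) p_s. It is zero if the shares agree or the sites do not differ.

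**3. Illustration A (assumed rates).** Five sites at 8, 10, 15, 20 and 22%, with DTG spread evenly: (8 + 10 + 15 + 20 + 22)/5 = 15%. The two highest sites average 21% and the other three 11%. The two lowest average 9% and the other three 19%. An even mix puts 40% of charts in any two sites. The rejection rates below are exact binomial enumerations of the uncorrected two-sided chi-square test at 0.05, with 92 against 92 and no drug effect.

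| Share of EFV charts from two extreme sites | EFV rate, two highest | Rejects | EFV rate, two lowest | Rejects |
|---|---|---|---|---|
| 40% (even) | 15% | about 5% | 15% | about 5% |
| 60% | 0.6 × 21 + 0.4 × 11 = 17% | 6.5% | 0.6 × 9 + 0.4 × 19 = 13% | 6.7% |
| 70% | 0.7 × 21 + 0.3 × 11 = 18% | 8.3% | 0.7 × 9 + 0.3 × 19 = 12% | 9.0% |
| 100% | 21% | 18.3% | 9% | 24.0% |

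**4. Illustration B (assumed rates).** One site differs from the other four and holds 20% of DTG participants.

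| Site rate vs the rest | EFV share at that site: 40 / 60 / 80% | Spurious difference (points) | Rejects |
|---|---|---|---|
| 15% vs 10% | EFV 12 / 13 / 14%, DTG 11% | 1 / 2 / 3 | 6 / 7 / 9% |
| 25% vs 10% | EFV 16 / 19 / 22%, DTG 13% | 3 / 6 / 9 | 9 / 20 / 36% |
| 25% vs 5% | EFV 13 / 17 / 21%, DTG 9% | 4 / 8 / 12 | 14 / 37 / 64% |

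**5. Does stratification repair it?** In 20,000 simulated studies per setting, with the last two rows of illustration B and the same imbalances, a Cochran-Mantel-Haenszel test stratified by site rejected in 4.7 to 5.1% of studies. Both groups were present at every site in these runs. A site with patients in only one group contributes nothing to a stratified test. In the 100% row of illustration A, three of the five DTG sites would drop out, which is 3/5 × 92, or about 55 of the 92 DTG participants.

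**The case against.** Several stronger readings are tempting, and the documents do not support them.

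- A reader might infer that DTG patients come from five cities while EFV charts come from somewhere else or from fewer places. Section 5 lists the sites for the whole study, directly after section 4 has included the record review in the design. The natural reading is that the same five sites supply both groups. The DTG group has no site quota either.
- A reader might take the section 11 sentence as a rule for EFV charts alone. It follows the sentence on the retrospective part, but it speaks of patients generally and can cover both groups. Consecutive selection is also a safeguard against picking charts by outcome. No document describes the order of chart abstraction, so filling the group from one convenient site is a possibility and not a stated plan.
- A reader might cite section 12.1, "Mortality rates are quite variable, depending on region, specific study, and population", as evidence that these five cities differ. The text that follows contrasts African with developed countries. It supports caution about region in general but says nothing about differences among the five cities.
- A reader might conclude that no later analysis could help. That is true only of sites with patients in one group. Where both groups are present, stratification is enough.
- The 18 to 24% figures need every EFV chart to come from the two most extreme sites. They are a worst case.

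It can also be said that this is declared an exploratory pilot, and that site alignment leaves the difference in calendar period untouched. Both are true. The first limits how much weight the result will carry, but section 12.3 still plans significance tests between the groups. The second is a separate problem and no reason to leave an avoidable one in place.

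What remains is the gap itself. Even if all five sites supply both groups, nothing aligns their proportions and nothing in the analysis accounts for a difference.

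**Conclusion.** The point holds as a gap in the plan. It is not evidence of an actual imbalance. Neither selection, nor the comparability table, nor the test for deaths takes site into account in a non-randomised comparison.

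The consequence depends on two things that the documents do not give: how far mortality differs among the sites, and how far the site shares of the two groups diverge. Under the assumed rates of 8 to 22%, a moderate divergence raises the false-positive rate from 5% to about 6.5 to 9%, and the extreme case raises it to 18 to 24%. If a single site differs by only 5 points, the rate is 6 to 9%. If it differs by 15 to 20 points, the rate runs from 9 to 64%, according to the share of EFV charts from that site. The direction cannot be predicted. The change is worth making because it is cheap and leaves the sample size alone.

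**What to change.** - In 7.1, state that EFV patients started antiretroviral therapy at one of the five study sites.
- In section 11, have each site abstract as many consecutive eligible EFV charts as it enrols DTG participants, and report any shortfall by site. State where consecutive selection starts. This also requires reconciling the EFV years, which are 2014-2016 in section 4 and 2013-2016 in 7.1.
- Add site to Table 1 in both documents.
- In Table 2 of both documents, replace the plain chi-square test for deaths with a site-stratified test such as Cochran-Mantel-Haenszel.

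The last change corrects an imbalance wherever both groups are present at a site. The per-site number secures that overlap.

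The cost is a few sentences and two table entries, and the total stays at 92 charts. The downside is that abstraction is spread over five sites and can close only once DTG accrual at each site is known. A site with too few eligible records will leave a shortfall. Confounding by calendar period remains and needs its own treatment.

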12.1. Sample Size Justification

Mortality rates are quite variable, depending on region, specific study, and population.

Most studies from African countries have shown that mortality in the first 3 months of ART for participants with CD4+ cells under the threshold of 50 cells/mm³ is generally greater than 30%, and may reach 52% in some reports.

On the other hand, in developed countries, most deaths in such a population usually occur after 7 months of therapy and the mortality rate is just as low (1.8% for the first year of treatment).

We estimated that early mortality for participants included in the EFV arm would be similar to the rates detected in African countries (around 30%). We hypothesize that participants using DTG-based regimens would benefit from faster recovery of CD4+ cell count and that they behave like those individuals starting antiretroviral therapy in developed countries (mortality rate around 2%).

Considering a lower limit of 2% (DTG arm) and an upper limit of 25% (EFV arm), a 95% CI and 80% power to detect differences between groups, it would be necessary to treat a total of 84 participants (42 on each arm). Adding 10% for dropouts, this would result in a total of 92 subjects (46 in each arm).

With the recent changes in treatment recommendations, all 92 participants will receive DTG. Participants who used EFV will be retrospectively evaluated, through the review of medical records, in an identical number (92 participants).

This will be an exploratory pilot study.

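### Is the study underpowered because its planning effect (2% vs 25% mortality) is larger than the poor-to-rich-country ratio the protocol cites?

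*Protocol*

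**What the plan says.** Protocol section 12.1 bases the calculation on "Considering a lower limit of 2% (DTG arm) and an upper limit of 25% (EFV arm), a 95% CI and 80% power". The two rates come from different settings. EFV participants are expected to die at rates seen in African countries, put at around 30% and lowered to 25% for the calculation. DTG participants are expected to do as well as patients in developed countries, at around 2%. The African figure describes "mortality in the first 3 months of ART for participants with CD4+ cells under the threshold", which is set at 50 cells/mm³; the developed-country figure (1.8%) is for the first year.

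The result is 42 per arm, raised to 46 for dropout (92 in total). The section then explains that, because treatment recommendations changed, all 92 will receive DTG, and 92 EFV records will be reviewed for comparison. It ends by calling the study an exploratory pilot.

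Section 3 cites a study whose "risk ratio for early death was 4.3 times higher (95% CI: 1.6 - 11 .8), in poorer countries". By the same account the gap narrows later in treatment, to a ratio of 1.5 beyond month seven. The section also cites a Brazil-USA comparison in which "the proportion of early deaths in the first three months was significantly higher for Brazilian participants compared to Americans". Section 5 names a centre in Bahia and says the study "will include 4 additional sites in different Brazilian cities". Neither document gives an absolute mortality rate for Brazil.

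**The concern.** Section 12.1 in effect assumes that DTG closes the whole gap between poorer and richer countries. Section 3 contains a direct estimate of that gap, and the planning ratio is 2.9 times the estimate and above its upper confidence limit. The EFV rate is carried from African cohorts to Brazilian clinics with no local figure behind it.

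The plan's own 2% multiplied by its own 4.3 gives an EFV mortality of 8.6%, about a third of the 25% assumed. If that were the truth, the mortality comparison would have roughly even odds, or worse, of detecting the difference, and a non-significant result could be misread as showing that the regimens do not differ. The EFV group is a record review matched to the DTG number, so enlarging it looks like an easy remedy.

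**Working it through.** **Inputs.** EFV 25%, DTG 2%, 80% power and 10% dropout (section 12.1); two-sided 5% test (section 12.3); final groups of 92 and 92 (section 12.1); cited ratio 4.3, 95% CI 1.6 to 11.8 (section 3). Deaths are compared by a chi-square test (SAP Table 2) with no statement on continuity correction, so power is given as uncorrected / corrected.

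**The plan's own figure.** The mean rate is (0.25 + 0.02)/2 = 0.135 and the difference is 0.23.
- n = [1.96 √(2 × 0.135 × 0.865) + 0.842 √(0.25 × 0.75 + 0.02 × 0.98)]² / 0.23² = (0.947 + 0.383)² / 0.0529 = 33.4, or 34 per arm without correction.
- With continuity correction: (33.4/4) × [1 + √(1 + 4/(33.4 × 0.23))]² = 41.7, or 42 per arm. This is the stated number.
- Dropout: 84 × 1.10 = 92.4, stated as 92.

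**The ratios.** 25/2 = 12.5, and 12.5/4.3 = 2.9. The planning ratio does exceed 11.8.

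**Power at the size actually planned.** Exact enumeration of the chi-square test at 92 vs 92, unadjusted:

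| EFV | DTG | Power |
|---|---|---|
| 25% | 2% | 99.9% / 99.8% |
| 25% | 5.8% (ratio 4.3) | 97% / 95% |
| 15% | 2% | 93% / 87% |
| 15% | 3.5% (ratio 4.3) | 81% / 71% |
| 12.5% | 2% | 83% / 73% |
| 12.5% | 5% | 45% / 32% |
| 10% | 2.3% (ratio 4.3) | 59% / 46% |
| 8.6% | 2% (ratio 4.3) | 51% / 38% |

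**Where power reaches 80%.**
- With DTG at 2%, EFV mortality must be at least 12.1% / 13.7%, a ratio of about 6.0 / 6.8.
- With EFV at 25%, DTG mortality may be as high as 9.6% / 8.8%, a ratio of about 2.6 / 2.8.
- With the ratio held at 4.3, EFV mortality must be at least 14.8% / 17.6%.

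The ratios in the first two lines lie inside the cited interval of 1.6 to 11.8. Whether 12.5 exceeds 11.8 therefore does not decide whether 92 vs 92 is enough.

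**Would more EFV records help?** With 184 EFV and 92 DTG at 8.6% vs 2%, power is 60% / 46%.

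**The case for a change.** The strongest case for acting is that the protocol has a mortality hypothesis, makes mortality its primary outcome, tests at two-sided 5%, and never restates power for the 92 vs 92 it will analyse. A reader cannot tell from section 12.1 that the comparison weakens quickly if EFV mortality is near 10%, or if DTG mortality is nearer 5% than 2%. One paragraph would show this. All of that is true, and such a paragraph would make the protocol better documented.

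The stronger reading, that the study is underpowered, does not stand.
- **The 8.6% is not a sound estimate.** It multiplies a first-year rate by a ratio for early death in participants with AIDS generally. Section 12.1 is open to the same criticism of mixing periods and populations.
- **Other figures in the protocol point higher.** Section 12.1 puts African three-month mortality at CD4+ below 50 generally above 30%, and as high as 52%. Section 3 gives a 4.8-fold risk of death at CD4+ below 50.
- **The difference in time windows does not inflate the EFV rate.** First-year mortality in a cohort cannot be lower than its three-month mortality, so 25% over a year is cautious relative to that source. Whether African rates apply to Brazil is the question that remains.
- **Extra EFV records bring little.** At the rates that cause the worry, doubling them still leaves power near even odds. They do nothing about confounding in a historical comparison, and the documents do not say how many eligible records exist.

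**Conclusion.** No change to the plan follows. The planning ratio of 12.5 is above the cited upper limit of 11.8, and the 25% has no Brazilian source; both observations are correct. But the stated 42 per arm is right for the stated rates, and the final design has about twice that number per group. The plan therefore falls short of no size or power that it claims. Power exceeds 99% at the planning rates and, with DTG at 2%, stays at 80% or more until EFV mortality drops to about 12% (uncorrected) or 14% (corrected).

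What remains is a gap in documentation. The 25% and 2% are assumptions, and a careful reader will treat them so, particularly in a study that calls itself an exploratory pilot. Labelling them, or adding a range of power values, would alter no analysis and correct no wrong number.

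This conclusion concerns deaths from any cause, compared without adjustment and with all 92 per group contributing. It does not cover the viral-load endpoint in section 12.5, confounding from the historical EFV group, or event rates that would arise if the failure algorithm in section 10.5 were applied to the mortality outcome.
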